### **Analytic Rationale**

As a large, pragmatic trial enrolling every adult admitted to the five participating intensive care units, the SMART study population will contain a wide spectrum of (1) exposure to the study intervention, (2) baseline risk of the primary outcome, and (3)

physiologically-distinct patient subgroups. The primary and secondary analyses evaluate the effect of the intervention overall and across the spectrum of exposure to crystalloid, baseline risk of MAKE30, and patient subgroups.

## Primary Analysis

To account for the cluster-level-allocation, cluster-level-crossover structure of the trial, the primary analysis will be an intention-to-treat comparison of the primary outcome of MAKE30 between the saline and balanced crystalloid groups using a generalized linear mixed-effects model including fixed effects (group assignment, age, gender, race, source of admission, mechanical ventilation, vasopressor receipt, diagnosis of sepsis, and diagnosis of traumatic brain injury) and random effects (intensive care unit)[27,28].

In preparation for SMART, we electronically collected the same set of variables that would be used to analyze SMART from the records of all 11,582 patients admitted to the study ICUs between January 1, 2014 and December 31, 2014. With the data on MAKE30 from the 11,582 patients admitted in the year before the trial, using generalized linear mixed-effects modeling treating the five ICUs as clusters and the 12 months as periods, we calculated the intra-cluster correlation coefficient to be 0.142, the intra-period correlation coefficient to be 0.026, and the intra-cluster intra-period correlation coefficient to be  $<0.001$ .

Using the data from the 11,582 patients admitted in the year before the trial, we performed a series of simulated trials evaluating a variety of trial conditions and potential results including: (1) outcome differences between groups ranging from no difference to a 50% relative risk reduction, (2) heterogeneity of treatment effect by cluster, (3) change in the incidence of the outcome in the control group over the course of the trial, (4) varying levels of intra-cluster correlation, and (5) varying levels of intra-period correlation. In each case the generalized linear mixed-effect model appeared to adequately account for the correlation between participants. Analysis using generalized linear mixed-effects modeling and generalized estimating equations accounting for the same variables produced identical odds ratios and 95% confidence intervals for the difference between the simulated groups in the primary outcome.

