### Study Aims:

- Primary: To compare the effect of saline versus balanced crystalloids on the development of major adverse kidney events within 30 days (MAKE30) in patients admitted to the intensive care unit
- Secondary: To evaluate the effects of the same intervention in the same population on secondary outcomes.

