## Population

All adults (age  $\geq 18$  years) admitted to a participating ICU at Vanderbilt University Medical Center during the study period are enrolled at the time of ICU admission. Enrolled patients who are discharged from the hospital are eligible again if they are admitted to a participating ICU again during the study period.

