## Primary Outcome

The primary outcome will be the proportion of patients meeting one or more criteria for Major Adverse Kidney Events within the 30 days after enrollment (MAKE30): in-hospital mortality, receipt of new RRT, or persistent renal dysfunction defined as a final inpatient serum creatinine value  $\geq 200\%$  of baseline[22–24]. In-hospital mortality will be defined as death from any cause prior to hospital discharge censored at 30 days after ICU admission. Receipt of new RRT will be defined as receipt of any modality of RRT between ICU admission and the first of hospital discharge or 30 days, among patients not known to have received RRT prior to ICU admission. Persistent renal dysfunction will be defined as a final serum creatinine value before hospital discharge (censored at 30 days after enrollment)  $\geq 200\%$  of the baseline creatinine value. The value for baseline serum creatinine will be determined using a previously-described hierarchical approach[22]. The lowest serum creatinine between 12 months and 24 h prior to hospital admission will be used when available. If no such creatinine value is available, the lowest creatinine value between 24 h prior to hospital admission and the time of ICU admission will be used. If no creatinine value is available between 12 months prior to hospital admission and the time of ICU admission, a baseline creatinine value will be estimated using a previously-described formula [creatinine =  $0.74 - 0.2$  (if female) +  $0.08$  (if African American) +  $0.003 \times$  age (in years)][25]. Patients known to have received RRT prior to enrollment will be considered ineligible to meet criteria for new RRT or persistent renal dysfunction, but may qualify for MAKE30 by experiencing in-hospital mortality.

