## Additional Secondary Analyses

We will perform the following additional secondary analyses:

- (1) Comparison of secondary outcomes between study groups.
- (2) Effect modification by severity of illness and pre-specified subgroups. Using generalized linear mixed effects modeling, we will examine the interaction between crystalloid assignment and the following baseline variables with respect to the primary outcome of MAKE30 in the intention-to-treat population:

- a. Source of admission to the ICU (Emergency department, Operating room, Transfer from another hospital, Hospital ward, Other)
- b. Study ICU (Medical, Surgical, Cardiac, Neurological, Trauma). [Because cluster cannot be treated as a random effect for this subgroup, we will use logistic regression modeling]
- c. Sepsis or septic shock (Yes, No)
- d. Traumatic brain injury (Yes, No)
- e. Receipt of mechanical ventilation (Yes, No)
- f. Receipt of vasopressors (Yes, No)
- g. Category of renal dysfunction at the time of enrollment (No renal dysfunction, Acute kidney injury, Chronic kidney disease, End-stage renal disease receiving RRT)
- h. Risk of in-hospital mortality as predicted by baseline University HealthSystem Consortium expected in-hospital mortality (continuous variable ranging 0.0 to 1.0)

(3) Sensitivity analysis excluding patients admitted in the week prior to a crossover ('washout'). We will repeat the primary analysis comparing MAKE30 between study groups in the intention to treat population excluding those admitted in the 7 days prior to a crossover in ICU crystalloid assignment (simulating a "washout" period). Prior data from the study ICUs suggests that less than 10% of patients remain in the ICU for longer than 7 days[14]. Excluding those admitted within 7 days of a crossover in ICU crystalloid assignment will allow use of a baseline factor to exclude the majority of patients who would go on to experience a crossover in crystalloid assignment due to the study design.

(4) Sensitivity analysis excluding patients who were transferred between ICUs or remained in the ICU through a crossover ('per protocol'). We will repeat the primary analysis comparing MAKE30 between study groups in the intention to treat population excluding those who remained in the intensive care unit through a crossover in crystalloid assignment or were transferred between study ICUs.

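### The primary MAKE30 model has no baseline renal covariate, although the data are already collected and prior-RRT patients can reach the composite only by death

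*Combined protocol and SAP*

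**What the plan says.** The final protocol (section 12, Primary Analysis), the SAP (Primary Analysis) and the published plan give the same covariate list: "fixed effects (group assignment, age, gender, race, source of admission, mechanical ventilation, vasopressor receipt, diagnosis of sepsis, and diagnosis of traumatic brain injury". The only random effect is intensive care unit.

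The aim is the effect "on the development of major adverse kidney events within 30 days (MAKE30) in patients admitted to the intensive care unit". There is no renal exclusion: adults "admitted to a participating ICU at Vanderbilt University Medical Center during the study period are enrolled at the time of ICU admission".

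Persistent renal dysfunction, one of three components, is "defined as a final inpatient serum creatinine value" at or above 200% of baseline (SAP, Primary Outcome). The preferred baseline precedes the admission: "The lowest serum creatinine between 12 months and 24 h prior to hospital admission will be used when available". Nothing requires the rise to follow enrollment. Patients known to have had RRT "will be considered ineligible to meet criteria for new RRT or persistent renal dysfunction"; they stay in the analysis and can count only through in-hospital death.

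Renal status is used elsewhere. Final protocol section 8.4.1 collects prior RRT, CKD stage III or greater and all creatinine values from 12 months before hospitalization. SAP Table 1 reports CKD, prior RRT and stage II or greater AKI. Item (g) of the subgroup list tests interaction with "Category of renal dysfunction at the time of enrollment (No renal dysfunction, Acute kidney injury, Chronic kidney disease, End-stage renal disease receiving RRT". That analysis is hypothesis-generating and leaves the primary estimate unchanged.

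**The concern.** For a kidney composite, renal status on arrival is a natural strong predictor. A patient on chronic dialysis has one route to the outcome instead of three. A patient arriving at 300% of baseline and leaving at 210% meets the creatinine criterion, while one arriving at baseline must first double. The model adjusts for ventilation, vasopressors, sepsis and brain injury but not for this.

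Two things are at stake. Prognostic variation that could be explained stays in the residual, which costs power. A chance difference in renal case mix between saline and balanced unit-months passes into the primary odds ratio, except where the other covariates happen to capture it. No planned sensitivity analysis of MAKE30 adds a renal term or restricts to patients below the threshold at entry.

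**Working it through.** **The plan's own figure.** Inputs from the SAP Power Calculation: 14,000 patients (7,000 per group assumed), MAKE30 about 15%, difference 1.9 points, two-sided 0.05. With 15.0% versus 13.1%, the pooled-variance standard error is sqrt(2 × 0.1405 × 0.8595 / 7,000) = 0.00587, and the unpooled one is also 0.00587. Then (0.019 − 1.96 × 0.00587) / 0.00587 = 1.275, giving power of 89.9%. The stated 90% reproduces, without a cluster term.

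**Power with and without a renal term.** The documents give neither prevalence nor group-specific risk, so these are assumptions. Each scenario has 14,000 patients, an overall control risk of 15% and a common odds ratio of 0.854 within renal groups. Simulated logistic models (600 runs, Monte Carlo error about 1.5 points) gave:

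| Dialysis | Entry AKI | Power without term | Power with term | Type I error, without / with |
|---|---|---|---|---|
| 2% | 5% | 90.0% | 90.3% | 5.2% / 5.2% |
| 5% | 10% | 83.3% | 86.3% | 3.3% / 3.7% |
| 5% | 15% | 78.5% | 85.3% | 4.3% / 5.0% |

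The last row can be checked in closed form, taking control risks of 15% (dialysis) and 50% (entry AKI):

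- Risk in the remaining 80%: (0.15 − 0.05 × 0.15 − 0.15 × 0.50) / 0.80 = 0.0844.
- Applying 0.854 within groups gives balanced-group risks of 0.0730, 0.1310 and 0.4606, overall 0.1340.
- Without the term: log odds ratio −0.131, SE sqrt[1/(7,000 × 0.1275) + 1/(7,000 × 0.1160)] = 0.0485, z = 2.71, power about 77%.
- With the term: the information from the three groups is 202 + 21 + 131 = 354, SE = 1/sqrt(354) = 0.0532, log odds ratio −0.158, z = 2.97, power about 84%.

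The check contains no other covariate and no clustering. What ventilation, vasopressors and sepsis already explain comes off the gain.

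**Chance imbalance.** Assume 12% enter with AKI at 40% risk. Risk in the others is (0.15 − 0.12 × 0.40) / 0.88 = 0.116. A 1-point imbalance moves the crude MAKE30 difference by 0.01 × (0.40 − 0.116) = 0.28 points, and 0.28 / 1.9 = 15% of the target. The patient-level standard error of the imbalance is sqrt(2 × 0.12 × 0.88 / 7,000) = 0.55 points, so 1 point is 1 / 0.55 = 1.8 standard errors. At prevalences of 5-15% and risk differences of 20-45 points, a 1.96-SE imbalance moves the difference by 0.14-0.53 points.

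**How well entry AKI can be seen.** SAP, Handling of Missing Data, gives pilot figures for 974 patients. Of these, 595 had a creatinine from 12 months to 24 hours before admission. For 259, baseline comes from the window between 24 hours before admission and ICU entry, so a doubling shows only if it occurred inside that window. The other 120 had no value. Entry AKI is poorly visible in (259 + 120) / 974 = 38.9%.

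**The case against.** The strongest reply is that the plan estimates a pragmatic intention-to-treat effect in all comers, says so, and examines renal status where it belongs. Item (g) gives effects by renal category, each MAKE30 component is reported separately, and Table 2 has a row for AKI arising after enrollment. Enrollment is now expected to reach 15,000-16,500, for which the formula above gives 91.8-94.0% power. All this stands and limits the importance of the point. None of it puts renal status into the primary estimate, though, and the AKI row is not MAKE30.

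A reader might infer from the word development in the aim that MAKE30 wrongly counts injury already present, so that the endpoint fails. The documents do not support that. The component measures persistence, and recovery below 200% is a legitimate thing for assigned fluid to affect. Patients arriving above the threshold can recover, start RRT or die; the restriction for prior-RRT patients is stated openly, and they remain at risk of death.

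A reader might also infer a validity problem, or a large loss of power from pooling. Type I error was 3-5% with or without the term, and chance imbalance is already part of the standard error. Large losses need an extreme case of no effect at all in either group: with 5% dialysis and 10% entry AKI (risks 15% and 50%), the pooled difference falls to 0.85 × 0.1088 × (0.019 / 0.15) = 1.17 points and power to about 50%. Nothing in the documents suggests that case. Converting explained variance on a linear scale into patients saved is no better, because the primary result is an odds ratio.

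A further objection concerns the covariate itself, and it stands. From January 2016, patients going from the ED to three of the ICUs received assigned fluid before ICU admission, as did operating-room patients where feasible (SAP, Study Interventions). The last creatinine before ICU admission can therefore follow exposure. Item (g) also does not say which creatinine defines its AKI level.

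**Conclusion.** The point holds as one of precision and chance imbalance. A kidney composite is analyzed without any baseline renal term, although suitable variables are in hand. The endpoint and the intention-to-treat population can stay as they are, and the test is valid without the change.

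The gain is about 0-7 points of power, resting on assumed prevalences of 2-5% for dialysis and 5-15% for entry AKI and on assumed risks; at the low end it is nil. The 0.28-point shift rests on 12% prevalence and a 40% risk, and the imbalance that produces it is fairly unusual. The standard error used for it treats patients as independent; clustering of entry AKI within unit-months would make such imbalances likelier, and the documents give no figure for that. The change is worth making because it is nearly free, not because the primary result is unsound without it.

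**What to change.** 1. Add an enrollment renal category (no dysfunction, AKI, CKD, prior RRT) as a fixed effect in the primary model. If the published model is not reopened, specify this as a named sensitivity model.
2. Code prior RRT and CKD from pre-enrollment data. Code entry AKI from the last creatinine before the earlier of ICU admission and the first assigned study fluid in the ED or operating room. Give patients with no separate pre-admission baseline a not-assessable level, and state which level takes precedence when two apply.
3. Add one supportive MAKE30 analysis among patients without prior RRT and not known to be at or above 200% of baseline at that time point. The covariate alone does not remove dysfunction present at entry from the outcome, so this analysis is needed for the question about new events.

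The cost is SAP wording and some coding; no new variable has to be collected. On pilot figures, up to about 39% of patients may fall in the not-assessable level for AKI. The supportive analysis has fewer patients. The adjusted odds ratio becomes conditional on renal category as well, so it should be read beside the unadjusted proportions already planned. The SAP labels any analysis outside it as post hoc, so without an amendment the added analyses must carry that label.

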## **8.4 Data Collection**

### **8.4.1 Data at Enrollment**

1. Study Enrollment Data:
  - a. Encounter Number ("Study ID")
  - b. Medical Record Number
  - c. Date and Time of ICU Admission ("Time Zero")
  - d. Study ICU at enrollment (Medical/Cardiac/Neuro/Trauma/Surgical)

Principal Investigators: [name], [name]

Version Date: 6/15/17

Study Title: Isotonic Solutions and Major Adverse Renal Events Trial (SMART)

Institution/Hospital: Vanderbilt University Medical Center

2. Demographic Data:

- a. Age (years)
- b. Gender (male/female)
- c. Race (White/Black/Asian/Alaskan/PacificIsland/Other)
- d. Ethnicity (Hispanic, Non-hispanic)
- e. Height (cm)
- f. Weight (kg)
- g. Date and time of Hospital Admission
- h. Source of admission to ICU (ED/OR/outside hospital transfer/hospital ward/outpatient/another ICU within the hospital)
- i. Admitting service
- j. ICD-9 and ICD-10 diagnoses

3. Comorbidities:

- a. Exlihauser comorbidities
- b. CKD stage III or greater by CKD-EPI criteria
- c. Prior receipt of renal replacement therapy
- d. Predicted risk of in-hospital mortality by University HealthSystem Consortium expected in-hospital mortality

4. Invasive Support:

The following information will be recorded during the 12 hours prior to and 24 hours following ICU admission (“Time Zero”). If more than one value is available for this 36-hour period, the value closest to the time of ICU admission (“Time Zero”) will be recorded.

- a. Receipt of Mechanical Ventilation (Y/N)
- b. Receipt of vasopressors (Y/N) (norepinephrine, epinephrine, dopamine, phenylephrine, or vasopressin)

5. Renal function

- a. All serum creatinine values from the clinical laboratory system between 12 months prior to hospitalization and 30 days after ICU admission
- b. Stage II or greater acute kidney injury by KDIGO creatinine criteria

6. Serum laboratory values

- a. All serum values for sodium, potassium, chloride, bicarbonate, and blood urea nitrogen between 12 months prior to hospitalization and 30 days after ICU admission

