### **Primary Analysis**

To account for the cluster-level-allocation, cluster-level-crossover structure of the trial, the primary analysis will be an intention-to-treat comparison of the primary outcome of MAKE30 between the saline and balanced crystalloid groups using a

Principal Investigators: [name], [name]

Version Date: 6/15/17

Study Title: Isotonic Solutions and Major Adverse Renal Events Trial (SMART)

Institution/Hospital: Vanderbilt University Medical Center

generalized linear mixed-effects model including fixed effects (group assignment, age, gender, race, source of admission, mechanical ventilation, vasopressor receipt, diagnosis of sepsis, and diagnosis of traumatic brain injury) and random effects (intensive care unit).

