### Power Calculation

Based on data from the study ICUs in the year prior to the trial, we anticipate the planned study duration (Figure 1) will result in enrollment of around 14,000 patients with an overall rate of MAKE30 around 15%. Enrollment of 14,000 patients will provide 90% power at an alpha level of 0.05 to detect an absolute difference between the saline and balanced crystalloid groups in MAKE30 of 1.9%, a relative risk reduction of 12%, which is comparable to the 12% relative risk reduction for in-hospital mortality reported in a recent pilot trial[13] (additional details in the Appendix 3).

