## TABLES

**Table 1. Patient characteristics at baseline.**

Patient Characteristics	Saline (n =)	Balanced (n =)
Age, median [IQR], years	--	--
Men, No. (%)	--	--
Caucasian, No. (%)	--	--
Weight, median [IQR], kg	--	--
Body mass index, median [IQR], kg/m 	--	--
Renal comorbidities, No. (%)		
Chronic kidney disease, stage III or greater	--	--
Prior renal replacement therapy receipt	--	--
Source of admission to ICU, No. (%)		
Emergency department	--	--
Transfer from another hospital	--	--
Hospital ward	--	--
Another ICU within the hospital	--	--
Operating room	--	--
Outpatient	--	--
Study ICU, No. (%)		
Medical	--	--
Surgical	--	--
Cardiac	--	--
Neuro	--	--
Trauma	--	--
Admitting diagnosis, No. (%)	--	--
Sepsis or septic shock	--	--
Traumatic brain injury	--	--
Mechanical ventilation, No. (%)	--	--
Vasopressors, No. (%)	--	--
UHC expected mortality, mean (95% CI), %	--	--
Serum creatinine, median [IQR], mg/dL		
Lowest in 12 months prior to hospitalization	--	--
No. (%) of patients	--	--
Lowest between hospitalization and ICU admission	--	--
No. (%) of patients	--	--
Estimated by three-variable formula	--	--
No. (%) of patients	--	--
Study baseline	--	--
Acute kidney injury, stage II or greater	--	--

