## Appendix 5: Handling of Missing Baseline Serum Creatinine Values

For patients without a measured serum creatinine between 12 months prior to hospital admission and enrollment, baseline creatinine value for the primary analysis will be estimated using a previously-described three-variable formula [creatinine = 0.74 – 0.2 (if female) + 0.08 (if African American) + 0.003 × age (in years)][25]. Multiple sensitivity analyses will employ alternative approaches to estimating missing baseline creatinine values:

- 1) A ‘complete cases’ analysis will be performed in which patients without a measured creatinine value between 12 months prior to hospital admission and enrollment will be excluded.
- 2) Missing baseline serum creatinine values will be imputed by multivariable single imputation using the R function `aregImpute` in `Hmisc` package with 5 imputations. The imputation model will include age, gender, race, group assignment, source of admission, primary diagnosis, receipt of mechanical ventilation, vasopressor receipt, prior hemodialysis, total fluids received in 30 days, UHC expected mortality, overall mortality, new RRT received, minimum creatinine value, maximum creatinine value, and final study creatinine value. Continuous variables will be transformed via cubic splines with 3 to 5 knots.
- 3) Simple imputation will be performed in which first serum creatinine value after enrollment is used as the baseline creatinine.
- 4) Simple imputation will be performed in which the highest serum creatinine value between enrollment and 30 days is used as the baseline creatinine.
- 5) Simple imputation will be performed in which the lowest serum creatinine value between enrollment and 30 days is used as the baseline creatinine.

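### The primary MAKE30 model omits UHC expected mortality, the plan's only continuous severity score; once its timing is confirmed, adding it should modestly improve precision

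*Combined protocol and SAP*

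**What the plan says.** The Primary Analysis section of the SAP, repeated in section 12.0 of the 6/15/17 protocol and in the published protocol paper, specifies a generalized linear mixed-effects model. Its fixed effects are "fixed effects (group assignment, age, gender, race, source of admission, mechanical ventilation, vasopressor receipt, diagnosis of sepsis, and diagnosis of traumatic brain injury". The only random effect is ICU. No reason is given for the choice of covariates.

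UHC expected mortality appears in four other places:

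- Protocol 8.4.1, Data at Enrollment: "Predicted risk of in-hospital mortality by University HealthSystem Consortium expected in-hospital mortality".
- SAP Table 1, as a baseline row: "UHC expected mortality, mean (95% CI".
- SAP Additional Secondary Analyses, item (2)h, as an effect modifier: "Risk of in-hospital mortality as predicted by baseline University HealthSystem Consortium expected in-hospital mortality (continuous variable ranging 0.0 to 1.0".
- SAP Appendix 5, in the imputation model for missing baseline creatinine: "total fluids received in 30 days, UHC expected mortality, overall mortality".

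It is the only continuous severity score in the current plan. APACHE II, SOFA and an electronic physiology score occur only in the superseded 2015 protocol.

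**The concern.** In-hospital death is one of the three MAKE30 components, so a score built to predict it should also predict MAKE30. The primary model carries severity markers, but apart from age they are yes/no or categorical, and so describe severity coarsely.

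Two things are at stake. The first is precision: a prognostic pre-treatment covariate raises the power of the treatment test in a logistic model without more patients. The second is residual imbalance. Five ICUs were assigned in two blocks by a single randomization and then alternate monthly. Severity can differ by chance between saline and balanced months, and the current markers remove only part of such a difference.

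The interaction analysis in item (2)h reports how the effect varies with the score. It does not improve the primary test.

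**Working it through.** **Inputs from the documents.** SAP, Power Calculation: "enrollment of around 14,000 patients with an overall rate of MAKE30 around 15"%, an absolute difference of 1.9 points, and "Enrollment of 14,000 patients will provide 90% power at an alpha level of 0.05". Tests are two-sided. I assume 7,000 patients per group.

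**1. Reproduce the stated power.** With 15.0% on saline and 13.1% on balanced crystalloids, the mean rate is 0.1405:

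Power = Φ{[0.019 − 1.96·√(2·0.1405·0.8595/7000)] / √[(0.15·0.85 + 0.131·0.869)/7000]} = 89.9%.

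The total N for 90% power is 14,056, against the stated 14,000. With 15% as the average of both groups (15.95% vs 14.05%), power is 88.3% and N is 14,842, which matches less well. The stated figure is therefore an unadjusted two-proportion calculation, with no covariate and no clustering term.

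**2. Gain from one more covariate.** Let R² be the variance of the predicted risks divided by p̄(1−p̄). Approximately:

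- effective-N factor g = (1 − R²_old)/(1 − R²_new)
- new power = Φ(3.235·√g − 1.96), where 3.235 = 1.275 + 1.96 corresponds to 89.9%

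The documents give no R² or AUC. I assume R² of 0.05 to 0.20 for the planned covariates and 0.01 to 0.10 added by UHC.

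| Added R² | g | Power, if the planned model has 89.9% | Detectable difference, 1.9/√g |
|---|---|---|---|
| 0.01 | 1.011–1.013 | 90.2% | 1.89 points |
| 0.02 | 1.022–1.026 | 90.5–90.6% | 1.88 points |
| 0.05 | 1.056–1.067 | 91.4–91.6% | 1.84–1.85 points |
| 0.10 | 1.118–1.143 | 92.8–93.3% | 1.78–1.80 points |

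Example: R² from 0.20 to 0.30 gives g = 0.80/0.70 = 1.143. Power is Φ(3.235·1.069 − 1.96) = 93.3%, a gain of 3.4 points. On 14,000 patients, 1% to 14% is about 140 to 2,000 effective patients.

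If 89.9% is instead read as unadjusted power, the planned covariates already lift it to 91.3–95.1%, and UHC adds a further 0.3 to 2.6 points.

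**3. Simulation check** (2,500 trials per setting, N = 14,000, 15.0% vs 13.1%, independent patients). When a second score raised R² from 0.076 to 0.088, power went from 92.4% to 92.7%. From 0.065 to 0.143, it went from 92.0% to 94.1%. For the second case the formula gives g = 0.935/0.857 = 1.091 and 94.0%.

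**4. When is the gain larger?** A second simulation (15.95% vs 14.05%) gave the existing covariates a logit-scale SD of 1.0 and the extra information in UHC an SD of 0.6, 1.0 or 1.4. Squared ratios of mean z-statistics were (3.42/3.33)² = 1.05, (3.49/3.27)² = 1.14 and (3.68/3.28)² = 1.26. The 26% gain needs extra variance of 1.4² = 1.96 against 1.0, so one score would add about twice the information of all existing covariates together.

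**5. Change of estimand.** The unadjusted odds ratio is (0.131/0.869)/(0.15/0.85) = 0.854. In simulation, the conditional odds ratio for the same two risks moved from about 0.84 to 0.83 as the second score was strengthened.

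**The case against.** The strongest reply is that this is a preference among covariates. The model already holds ventilation, vasopressors, sepsis, traumatic brain injury, admission source and ICU. The 90% power statement holds without any covariate. At the 15,000 to 16,500 patients later anticipated, unadjusted power is already 91.8% to 94.0%. That stands as a limit on the size of the gain; it is no reason to leave the score out.

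Timing is the more serious point. The documents do not say when or from what data the score is computed. The superseded 2015 protocol listed observed/expected ratios under data at termination. If post-enrollment information enters the score, adjusting for it could bias the primary effect. This stands and makes confirmation a precondition. The plan needs that confirmation in any case, because item (2)h relies on the score being baseline.

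The change would also follow publication of the SAP and its code, completion of both interim analyses, and a statement that analyses outside the SAP count as post hoc. A dated amendment before any unblinded final analysis, with the current model retained, answers this.

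Finally, the protocol paper refers to an additional file on development of the primary model, so a reason may exist there. I can say only that the documents at hand give none.

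**Conclusion.** The point holds as a modest improvement. Under the assumed range, adding the score is worth about 1% to 14% more effective patients, or 0.3 to 3.4 points of power. These figures rest on assumed R² values and ignore clustering.

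A reader might infer more, and the documents do not support it:

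- *That the gain costs nothing.* Neither the score's inputs nor its completeness is stated, and no present-at-admission version is described.
- *That the trial is underpowered without it.* The stated power reproduces with no covariate.
- *That severity differences go uncorrected.* Existing markers correct for them in part. The SAP argues that frequent crossovers balance characteristics, and it reports an intra-cluster intra-period correlation below 0.001 for MAKE30 in the 2014 data. Only residual imbalance is at issue, and the simulations of independent patients do not measure it.
- *That omission biases the effect toward the null.* The shift in the odds ratio is non-collapsibility. The difference in risks is unchanged.

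**What to change.** Before any unblinded final analysis:

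1. Confirm that UHC expected mortality uses only information fixed before assignment can affect it, and state how many patients have a score.
2. Estimate its added prognostic value in the 2014 data set of 11,582 patients, which the SAP describes as holding the same analysis variables. This uses no trial outcomes.
3. If timing and completeness are acceptable, amend the SAP to add logit(UHC expected mortality) to the fixed effects of the primary model and of the binary secondary-outcome models. Truncate the score at 0.001 and 0.999, since the logit is undefined at 0 and 1, and include an indicator for a missing score. Keep the current model as a sensitivity analysis.
4. If the inputs cannot be confirmed as pre-enrollment, use the score only in a sensitivity analysis.

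The cost is the check on the score, a short amendment to the SAP and matching protocol text, and a small change to the R code. No extra patients are needed. Some scores may be missing, and the conditional odds ratio changes slightly, so the report should say which covariates it conditions on.
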